The proposed study is a longitudinal (9-month) RCT in which primary caregiver parents (as defined in inclusion criteria) of technology-dependent children will be randomly assigned to one of two study arms: (1) The **Attention Control arm** will receive weekly phone calls for the first 4 weeks and at 2 and 4 months post-enrollment plus the current standard of care, whereby caregivers phone their healthcare providers when they have questions or concerns; and (2) The **Resourcefulness Training[©] arm** will receive (a) individually tailored instruction on personal and social resourcefulness skills via the Resourcefulness Video and interventionist, (b) instruction for the online log-writing (via REDCap) so for the parent to describe resourcefulness application, (c) access to the study website with videotape vignettes and Resourcefulness Video, and (d) boosters at 2 and 4 months post-enrollment that will include reinforcement of skills learned and additional online log writing. Measures of parents' outcomes (mental and physical HRQoL, depressive cognitions, depressive symptoms, appraised stress, and burden) and self-management behaviors (appraised/objective sleep, positive health practices) will be obtained at enrollment (T1), then 6 weeks (T2), 3 months (T3), 6 months (T4), and 9 months (T5) post-enrollment to analyze the immediate, extended, and long-term effects of the intervention on parents' outcomes. Chronic stress will be measured by obtaining parents' hair cortisol levels and objective sleep by actigraphy at T1, T3, T4, and T5 to examine changes over time. We will also obtain measures of the mediating (personal and social resourcefulness) variable and covariates (caregiver's race/ethnicity, gender, family income, duration of caregiving, child's functional status, and type of technology).

Research Procedures. The Project Director will notify the data collector of potential participants. He/she will schedule an appointment at a mutually agreed upon time and in a private place of the parent's choosing (e.g., parent's home, library). At that meeting, the data collector will have the parent read the consent form and answer any questions. After written, informed consent is obtained, the data collector will collect baseline (T1) data (questionnaires),

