and afterwards collect a hair sample (at the place of the data collection visit) for hair cortisol analysis from the vertex of the parent's head using a standardized protocol.⁹⁰ Next, the data collector will instruct the parent regarding the Actiwatch (Philips Respironics, Bend, OR) protocol to measure sleep patterns. This includes application of the Actiwatch on the non-dominant wrist during the enrollment visit with instructions to wear it continuously for 10 days in order to capture baseline sleep patterns. Parents will also receive instructions on a sleep history booklet that will supplement Actiwatch actigraphy data during sleep pattern analysis (e.g., reason for night awakenings). Following data collection, the Project Director will log into a secured database and receive the subject's randomly assigned study arm (Attention Control or Resourcefulness Training). Data collectors will be blinded to all participants' study arm assignment. Randomization will be performed using Minim,⁹¹ a computer minimization stratified randomization program. Minimization helps achieve balance in treatment assignment within strata for targeted covariates.⁹² Stratification variables are sex (female, male), race/ethnicity (White non-Hispanic, all others), and OTA³² group (mechanical ventilator, intravenous nutrition/medication, or respiratory/nutritional support). In keeping with the good clinical practice policy (NOT-OD-16-148), the PI will ensure that all key personnel and staff obtain the Good Clinical Practice Training. The Graduate Student RA will keep a list in our NIH Regulatory Binder.

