Attention Control arm. The Attention Control arm will receive study attention via in-person contact at T1, T3-5, weekly phone calls from the Project Director (2-4 minutes) for the first 4 weeks, then phone calls at 2 and 4 months after enrollment to maintain consistency with the intervention arm. The Project Director will ask parents to describe how they/their child are doing. These calls will help to build a relationship with subjects to promote study retention. We recognize that in this group parents may obtain self-initiated caregiving information and support, which will vary among this group. We will use the Information and Support Form to monitor their acquisition of information and support at 6 weeks, 3 months, 6 months, and 9 months post-enrollment. While usual care may vary depending on the healthcare providers seen, all parents assigned to this group can call a physician or nurse to ask specific questions as needed.

Resourcefulness Training Intervention[®] arm. After we collect T1 data, the interventionist will schedule an appointment to conduct the initial instruction for the RTI[®] during a session lasting approximately 1 hour either face-to-face in a private place of the parent's choosing or via Zoom using a computer, tablet or smart phone. The interventionist will also conduct all intervention arm follow up.

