sessions. Thereafter, all of the initial intervention sessions will be audio recorded, and the PI and will randomly select 30% of the recordings to monitor for the delivery, receipt, and enactment of the interventions, evaluating them using an intervention fidelity checklist based on the guidelines of Bellg et al.¹⁰¹ All intervention participants who have audiotaped fidelity checks will be asked to sign a GM-23 consent form prior to any audiotaping.

For participants who receive their intervention session via Zoom will be contacted by the interventionist when scheduled for the intervention appointment that they will need to sign a consent form. If in agreement, emailed a GM-23 consent form via REDCap to be signed prior to the audiotaped intervention session. If any participant refuses to consent it will be noted in the REDCap form. Retraining will occur if 100% accurate delivery of the intervention is not achieved. Once enrollment has begun, the Project Director and [name] will hold weekly supervision meetings with the interventionist and data collectors to address questions or concerns. Logs will be analyzed for the number of days entries were completed, as well as the number, type, and exemplars of each resourcefulness skill. [name], who has used journals and diaries^{102,103} in mixed-methods research with grandmother caregivers in addition to our pilot study, will oversee content analysis. Fidelity will also be assessed by noting increasing scores on the Resourcefulness Scale¹⁰⁴ and Resourcefulness Skills Scale⁸⁶ over time.

Fidelity of the Intervention (Subject). Fidelity of the intervention (uptake) for each subject (i.e., parent) will be measured 3 ways. First, the 8-item Resourcefulness Skills Scale will determine the frequency of use of resourcefulness skills taught in the intervention.⁸⁶ Higher scores indicate greater use. Second, journals for the intervention arm will be analyzed for resourcefulness skills use after the initial 4-week journaling period. In addition, we will analyze journals after each booster session. Finally, the Information and Support Use Form¹⁰⁵ will be used to measure information and support that a parent may have received during the 9-month study period that may affect outcomes for either group.

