Aims 1 & 3: Analysis of the monthly rate of change for each parent outcome in each arm will be estimated via linear mixed models and fit using SAS PROC MIXED.^{128,129} Each model will include a random intercept and slope (possibly modeled using a polynomial spline) to account for between-subject variance in each outcome over time. Conditional on these random effects, we will explore within-subject variance in each outcome over time using different residual covariance structures and select the most appropriate structure using likelihood-based criteria. Fixed effects will include a continuous variable to represent time since randomization, an indicator variable to represent the intervention, and stratification factors used during randomization (facility, OTA technology group, race/ethnicity). Assuming a linear rate of change over time, the regression coefficient of the terms representing interactions between time and the intervention indicator variable will be used to estimate the difference in the monthly rate of change in each outcome between arms.

Aim 2 & 4: To determine if resourcefulness mediates the effect of the RTI[©] on parent outcomes (psychological and physical health, self-management behaviors), a theory-based causal mediation model^{130,131} will be fit using separate linear mixed models of parent outcomes at 3 months after randomization that adjust for the intervention indicator variable, stratification factors, and the mediator at 6 weeks after randomization. This model will allow us to decompose the total effect of the RTI on parental outcomes at 3 months into direct and indirect (or mediated) effects and estimate the proportion of the total effect that is mediated. Variance estimates and 95% confidence intervals will be estimated using a bootstrapping procedure based on 1000 bootstrap samples. To more fully explore the temporal pattern of mediated effects, we will use similar models to estimate the mediated effect using measurements of the mediator and parental outcome taken at other time points as well (e.g., total effect of RTI[©] on parent outcomes at 6 months that are mediated by personal and/or social resourcefulness at 3 months).

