All participants are volunteers and non-participation and withdrawal from the study are alternatives to study participation. Parents will be told that they may withdraw from the study at any time. There are no risks to non-participation or withdrawal from the study. The Project Director (at recruitment) and the data collectors (at enrollment) will explain that participation or non-participation will have no effect on the type, quality, or nature of medical care that the technology-dependent child receives, and that all research data will be obtained by an Interventionist or data collector and will not be communicated to any healthcare personnel at the healthcare facility.

Writing about the stress of caring for their child in their journal might bring out uncomfortable feelings. Parents will be instructed that if they experience distress, they may stop the journaling and contact the research staff. In addition, they will be instructed to tell the research staff about these feelings during the weekly follow-up telephone calls. If needed, we will provide emotional support and refer them to mental health resources such as the 24-Hour Mental Health Crisis, Information and Referral Hotline as detailed in the above description of risks. We have past experience teaching journal writing, analyzing journal entries, and reviewing entries for psychological distress. To minimize potential problems, we will collect journals after 1 month. Drs. [name] and [name], psychiatric-mental health nurses, will oversee online log writing analysis for high-risk mental health situations, and follow up as needed. In past experience with journal writing, no psychological distress has occurred. Additionally, we will make weekly follow-up phone calls for the first 4 weeks of the intervention to monitor for signs of psychological distress.

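### One unblinded role hands candidates to enrolment, receives every allocation and calls the control arm under minimisation with no stated random element, so the next arm may be guessable above chance at hand-off

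*Combined protocol and SAP*

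**What the plan says.** The protocol gives the Project Director these tasks:

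- **Recruitment contact.** In the paragraph on voluntary participation, within the discussion of risks: "The Project Director (at recruitment) and the data collectors (at enrollment) will explain" that the decision to take part does not affect the child's care.
- **Hand-off.** Research Procedures: "The Project Director will notify the data collector of potential participants"; scheduling, consent and T1 follow.
- **Allocation.** Same section, after T1: "the Project Director will log into a secured database and receive" the assigned arm. No other role is named for this step.
- **Control-arm contact.** Attention Control arm: "weekly phone calls from the Project Director (2-4 minutes) for the first 4 weeks", then calls at 2 and 4 months.
- **Supervision.** Ensuring Fidelity of the Intervention (Interventionist): the Project Director and a colleague "will hold weekly supervision meetings with the interventionist and data collectors to address questions or concerns".

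The allocation tool, Minim, is described as "a computer minimization stratified randomization program". "Stratification variables are sex (female, male), race/ethnicity (White non-Hispanic, all others), and OTA" group, the last with three levels. No assignment probability is given. Data collectors are to be blinded to arm; nothing similar is said of the Project Director, and no step keeps past allocations from those who recruit. The analysis text for Aims 1 and 3 gives a different factor list: "stratification factors used during randomization (facility, OTA technology group, race/ethnicity", with facility in place of sex.

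**The concern.** Drawing the arm after consent and T1 hides the draw itself. It does not hide what the draw is likely to be. Under minimisation the next assignment depends on the running totals for that candidate's factor levels, and the person who receives each arm has seen everything that makes up those totals. If that person also passes candidates to enrolment, the order, timing or vigour of referral can follow the expected arm, even unintentionally.

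At stake is comparability on traits that are not minimised, such as motivation, distress or time for the daily log. The mixed model adjusts for arm, time and the stratification factors, so it would not remove an imbalance of that kind.

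**Working it through.** The plan gives no figure for predictability, so there is none to reproduce. The size was assessed by simulation.

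**Inputs from the protocol.** N = 210, 1:1 (Sample Size and Justification); three factors with 2, 2 and 3 levels (Research Procedures).

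**Assumptions not in the protocol.** Equal factor weights; ties broken at random; probability p of assigning the arm that reduces imbalance; three factor mixes (female 70-95%, White non-Hispanic 50-80%, technology groups from equal thirds to 10/5/85%); 300 runs per setting.

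**Rule.** For each candidate, d = the sum over the three factors of (number in training arm − number in control arm) at that candidate's level. If d ≠ 0, the arm with the lower total is assigned with probability p; if d = 0, the arm is a coin toss. The guesser names the arm with the lower total.

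**Step 1: all factors and current totals known.** Share correct = P(d ≠ 0) × p + P(d = 0) × 0.5. For the mix with 85% female, 70% White non-Hispanic and groups 20/10/70%:

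| p | P(d ≠ 0) | Formula | Simulated |
|---|---|---|---|
| 1.0 | 0.798 | 0.798 + 0.202 × 0.5 = 0.899 | 0.898 |
| 0.9 | 0.829 | 0.746 + 0.171 × 0.5 = 0.832 | 0.829 |
| 0.8 | 0.860 | 0.688 + 0.140 × 0.5 = 0.758 | 0.758 |
| 0.7 | 0.896 | 0.627 + 0.104 × 0.5 = 0.679 | 0.676 |
| 0.5 | – | simple randomisation | 0.50 |

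The other two mixes agree to within 0.01.

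**Step 2: less knowledge, p = 1.0.** Without race/ethnicity, about 82% correct. With technology group only, about 70%.

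**Step 3: stale totals.** Referral comes before the draw, so the relevant guess uses totals k allocations old. With 20% male, 30% not White non-Hispanic and groups 20/5/75%:

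| k | p = 1.0 | p = 0.8 |
|---|---|---|
| 0 | 90% | 76% |
| 1 | 56% | 63% |
| 2 | 63% | 62% |
| 3 | 54% | 58% |
| 5 | 53% | – |

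The protocol does not give k. These figures depend on the mix more than those in step 1: rerunning the same simulation for the two most extreme mixes gave about 43% to 67% for k = 1 to 5 at p = 1.0. They describe someone who simply reads the old totals. A guesser who anticipates the intervening parents would do better.

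**Step 4: what a guess could do (illustration only).** Suppose parents expected in the training arm are 0.1 SD better on an unminimised trait and those expected in control 0.1 SD worse. With share correct a, the arms then differ by 0.2 × (2a − 1) SD:

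- a = 0.898: 0.2 × 0.796 = 0.16 SD
- a = 0.758: 0.2 × 0.516 = 0.10 SD
- a = 0.53 to 0.63: 0.2 × 0.06 to 0.2 × 0.26 = 0.01 to 0.05 SD

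The 0.1 SD drift is an assumption; nothing in the protocol suggests its size.

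**The case against.** The strongest reply is that the protocol shows less control and less knowledge than the worst case needs.

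- **Approach.** A reader might infer that the arm can be predicted before a parent is approached. The recruitment text does not support this: clinic, Akron and Cleveland Clinic staff, school nurses, mailed letters and self-referral often come first. The step tied to the Project Director is the notice to data collectors, and no discretion over its order or timing is described.
- **Knowledge of factors.** Race/ethnicity is recorded on the enrollment form and technology type on a T1 questionnaire. Akron forwards contact details only. Record prescreening makes earlier knowledge plausible for some parents and does not establish it for all.
- **Determinism.** A reader might also infer that Minim runs without a random element. The protocol does not say either way; silence on the probability is a reporting gap.
- **Timing.** Scheduling, consent, questionnaires, hair sampling and Actiwatch set-up lie between hand-off and draw, and other parents may be allocated meanwhile. The 90% figure is a ceiling.
- **Safeguards.** Consent and T1 are completed first, by data collectors who are to be blinded, and the arm comes from a secured database.

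All of this stands and narrows the point. It does not remove it. The safeguards protect consent and baseline data, and the database conceals the next draw, but neither hides the history its user has already received. Technology group alone, which bears directly on eligibility, can lift the guess above chance when totals are current.

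**Conclusion.** The concern holds as a weakness in allocation concealment arising from combined roles. One role not described as blinded covers recruitment contact, hand-off, receipt of every allocation, control-arm calls and part of the interventionist's supervision, under a three-factor minimisation with no stated random element. That person may be able to guess the next arm above chance before the hand-off.

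The size runs from about 90% correct at best, through about 76% at 80:20, to about 53-63% when one to five allocations intervene, against 50% by chance. The first two figures hardly move across the assumed factor mixes. The last belongs to one mix and varies with it. All rest on equal weights and on the guesser knowing the factors.

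The remaining risk is selective or re-timed referral. A reader might go on to infer that the comparison is biased or that referrals will be steered. The protocol gives no evidence of either, and predictability alone is not bias. The point merits a change because the role conflict is written into the plan and can be separated cheaply.

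**What to change.** In Research Procedures and the Attention Control arm text, assign recruitment contact and the hand-off to an existing staff member who does not draw allocations, see past assignments, make control-arm calls or supervise the interventionist. Alternatively, leave recruitment and hand-off with the Project Director and move those other tasks elsewhere. State who may see the running allocations.

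As a secondary measure, run Minim with a random element and state its probability. An 80:20 setting is one example. It lowers the best-case guess from about 90% to about 76% and does not bring it to chance, so role separation matters more.

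While editing, reconcile the factor list in Research Procedures (with sex) with the one under Aims 1 and 3 (with facility).

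The cost is reassignment of a task, one software setting and slightly looser balance on the minimised factors.

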We recognize that, with writing, some will share disconcerting feelings. We have past experience teaching journal writing, analyzing log entries, and reviewing entries for psychological distress. To minimize potential problems, we will review REDCap logs after 1 month. Drs. [name] and [name], psychiatric-mental health nurses, will oversee journal analysis for high-risk mental health situations, and follow up as needed. In past experience with journal writing, no psychological distress has occurred. Additionally, we will make weekly follow-up phone calls for the first 4 weeks of the intervention to monitor for signs of psychological distress.

Booster sessions of RTI[©] will be delivered at 2 and 4 months post-enrollment to refresh the subject's memory of resourcefulness skills and prevent decline in skill usage.⁹⁸⁻¹⁰⁰ Booster sessions will be conducted in 10-minute telephone calls. The interventionist will record the parent's recall of skills learned, review skills that have been forgotten, determine whether he/she still has and uses the reminder card and magnet, ask for examples of skill application since the last study contact and which skills were used most often and were the most helpful, and collaboratively plan approaches to promote continued skill application. Parents who are unable to locate the reminder card and/or magnet will be mailed a new one. Because practice is an important component of this intervention, we will ask them to begin 1 week of daily REDCap log as they did for the initial RTI. We will phone them one week after each booster session (2-3 minutes) to inquire about their use of the REDCap log and answer questions about application of resourcefulness skills.

Ensuring Fidelity of the Intervention (Interventionist). Drs. [name] and [name] will use a systematic procedure to train the interventionist and monitor standardized administration of the RTI[©]. Examples of each resourcefulness skill and instructions for intervention delivery will be included in the written protocol and given to the interventionist. Before enrollment begins, the interventionist will have two practice sessions with student volunteers, who will present typical problems and questions they may encounter, to assess intervention fidelity. The PI will monitor the first 3 consecutive intervention

sessions. Thereafter, all of the initial intervention sessions will be audio recorded, and the PI and will randomly select 30% of the recordings to monitor for the delivery, receipt, and enactment of the interventions, evaluating them using an intervention fidelity checklist based on the guidelines of Bellg et al.¹⁰¹ All intervention participants who have audiotaped fidelity checks will be asked to sign a GM-23 consent form prior to any audiotaping.

For participants who receive their intervention session via Zoom will be contacted by the interventionist when scheduled for the intervention appointment that they will need to sign a consent form. If in agreement, emailed a GM-23 consent form via REDCap to be signed prior to the audiotaped intervention session. If any participant refuses to consent it will be noted in the REDCap form. Retraining will occur if 100% accurate delivery of the intervention is not achieved. Once enrollment has begun, the Project Director and [name] will hold weekly supervision meetings with the interventionist and data collectors to address questions or concerns. Logs will be analyzed for the number of days entries were completed, as well as the number, type, and exemplars of each resourcefulness skill. [name], who has used journals and diaries^{102,103} in mixed-methods research with grandmother caregivers in addition to our pilot study, will oversee content analysis. Fidelity will also be assessed by noting increasing scores on the Resourcefulness Scale¹⁰⁴ and Resourcefulness Skills Scale⁸⁶ over time.

Fidelity of the Intervention (Subject). Fidelity of the intervention (uptake) for each subject (i.e., parent) will be measured 3 ways. First, the 8-item Resourcefulness Skills Scale will determine the frequency of use of resourcefulness skills taught in the intervention.⁸⁶ Higher scores indicate greater use. Second, journals for the intervention arm will be analyzed for resourcefulness skills use after the initial 4-week journaling period. In addition, we will analyze journals after each booster session. Finally, the Information and Support Use Form¹⁰⁵ will be used to measure information and support that a parent may have received during the 9-month study period that may affect outcomes for either group.

Intervention Exit Survey. A brief 10-15 minute survey will be administered via REDCap to participants who meet the following eligibility criteria: 1. randomized to the intervention arm; 2. completed the intervention and follow up data collection points; and 3. have not asked to withdraw from the study. This brief survey includes questions about the intervention such as what the easiest/most challenging part was, ways we could make the Resourcefulness Training[®] better in the future. Eligible participants will be notified (no more than 3 attempts) of the opportunity to complete the Intervention Exit Survey using their preferred mode of contact used in the study and told, that participation is voluntary. If they agree to complete the intervention exit survey, we will inform them of the need to sign a consent form that includes the extra procedure; completion of the intervention exit survey. We will email them the REDCap link for the consent form and once they have signed the consent they will proceed to the intervention exit survey.

Data Collection. The data collectors will collect baseline data (T1) using 12 questionnaires to obtain demographic characteristics of the parent and technology-dependent child and to measure the parental outcomes, self-management behaviors, mediating variables, covariates, and descriptive variables (Table 2). Based on previous experience, this will take about 45 minutes. Following questionnaire completion, a small hair sample from the vertex of the head will be collected, taped, labeled, and placed in foil using a standardized protocol.⁹⁰ At the conclusion of the data collection, each subject will be instructed on the use and application of the Actiwatch device for 10 days. Past studies found 9% of nights not scored due to artifact or device not worn.¹⁰⁶ Instructions regarding Actiwatch (and sleep history booklet) return to the study office in the self-addressed, postage paid envelope will be given. Subjects will also be given a sleep history booklet and instructed to record the time they went to bed and woke up, number and reason for night awakenings, and naps. Sleep history booklets have been used in past studies for agreement and interpretation of actigraphy findings; 3-10% were excluded due

to non-compliance.¹⁰⁷ They will be asked to think of a place to keep the sleep history booklet that will serve as a reminder. Participants will be mailed a \$5 gift card each time they return the Actiwatch and sleep history booklet to the study office (baseline and 3month, 6 months, 9 months post baseline).

Follow-Up Contacts and Data Collection. Data will be collected for both study arms via mailed questionnaires, emailed link to REDCap surveys (depending on participant preference) at approximately 6 weeks (T2) after the initial delivery of the Resourcefulness Training Intervention or enrollment for the control group. Reminder phone calls will be made by data collectors if questionnaires are not completed within 2 weeks. Data collectors will obtain data about informational, social, caregiving support they may have received related to care of the technology-dependent children at (e.g., phone calls to healthcare providers, amount and type of Internet usage to obtain information, social support or lay caregiving, home nursing) using the Information and Support Form by phone at T2 and in person T3-T5 (3, 6, 9 months post-enrollment). Data collectors will also meet with parents face-to-face at T3-T5 to collect questionnaire data, obtain hair samples, and reapply the Actiwatch and will be blinded to group assignment. Table 2 details timing for all measures. In addition, the interventionist will phone the intervention arm subjects weekly for the first 4 weeks post-enrollment for the initial intervention and at 2 and 4 months post-enrollment for the booster sessions. To maintain consistency of contact with the intervention group, the Attention Control arm will receive weekly phone calls from the Project Director for the first 4 weeks post-enrollment, and then at 2 and 4 months after enrollment. We will also invite eligible intervention arm participants to complete the Intervention Exit Survey (see section Intervention Exit Survey above). If a parent asks a question about the care of their children, they will be referred to their healthcare provider.

Technology-Dependent Child Death. If a technology-dependent child dies during the study period, the Project Manager will send a condolence card to the family and obtain descriptive data about the date and cause of the child's death in the Electronic Medical Record. Data regarding the technology-dependent child's death will not be collected by ACH staff.

Children Who No Longer Require Technology. Parents whose children no longer require medical technology will remain in the study, and their data will be analyzed separately.⁴¹ We will document how soon after study enrollment the technology was discontinued. We expect about 5% will have technology discontinued and thus we will enroll additional participants to compensate for this attrition.

Retention Plans. To maximize retention over the 9 months, we will send birthday cards on the parent's and child's birthdays, as well as bi-monthly postcards with an inspirational message and contact information for the study office. Furthermore, we will recruit data collectors who are experienced and comfortable working with families who have children with special needs.

Controlling diffusion of intervention approaches. In our prior work, we found that few participants knew one another, so we believe the threat of diffusion is low. We recognize the possibility of the Hawthorne effect impacting our data. Therefore, the research team believes that it is vital to reliably track the amount of information and emotional support obtained by parents in all study arms and expect that any Hawthorne effect will be equally distributed because we are collecting the same information for both arms.

Measures. Study measures will be obtained at baseline (study enrollment), 6 weeks, and 3, 6, and 9 months post-enrollment, time frames selected based on prior work with caregivers and RTI[®] in order to capture variability over time. Table 2 shows study measures and measurement points. We chose measures based on our prior work with caregivers that are psychometrically sound and/or recommended by NIH as common data elements to facilitate cross-study analysis and increase the scientific impact of our study analyses.

Parent Outcome Variables: Parent Mental and Physical HRQoL will be measured by the 10-item Patient-Reported Outcomes Measurement Information System (PROMIS[®]) Short Form v.

1.2 Global Health Scale.^{108,109} The PROMIS[®] measures have been extensively tested and demonstrate excellent psychometric properties. Depressive cognitions will be measured by the 8-item Depressive Cognitions Scale¹¹⁰ to assess cognitive symptoms that precede depression;¹¹¹ higher scores indicating more depressive cognitions.^{110,112} Depressive symptoms will be measured by the 8-item PROMIS[®] Short Form v 1.0-Depression 8a.¹¹³ A clinically significant *T* score of 60 (raw score ≥ 22) requires action steps (see Human Subjects).¹¹⁴ Appraised stress (subjective) will be measured by the 10-item Perceived Stress Scale¹¹⁵ (NIH Toolkit); higher scores indicate greater stress. The level of chronic stress will be measured by a hair cortisol sample that measures cortisol level over the past 3 months.^{68,90,116} Caregiver burden will be measured using the Zarit Burden Interview-12, a 12-item tool assessing caregiver burden, with higher scores indicating higher burden.¹¹⁷ While originally developed for caregivers of older adults, it has been successfully used with parent caregivers.^{118,119}

Self-Management Behaviors: Appraised sleep quality will be measured by the Pittsburgh Sleep Quality Index (PSQI), a 19-item, self-report measure of sleep disturbance in adults.¹²⁰ It provides a global score that includes 7 subscale scores: sleep quality, sleep duration, sleep latency, sleep disturbance, habitual sleep efficiency, daytime dysfunction, and sleep medications over the past month. A global sum of ≥ 5 indicates a “poor” sleeper.¹²⁰ Objective sleep patterns (total sleep time, wake after sleep onset [WASO], sleep latency [time to fall asleep], sleep efficiency [% of time spent in bed sleeping], longest sleep period, night-to-night instability [mean square successive differences])⁴ will be measured using the Actiwatch (Philips Respironics, Bend, OR) for actigraphy. Actigraphy is a valid and reliable measure of sleep that is highly correlated with the clinical gold standard, polysomnography,^{121,122} but more practical for caregivers. The Actiwatch contains a calibrated accelerometer that can interface with a

Table 2. Variables and Measures

VARIABLE	MEASURE	TIME OF MEASURE
Parent Outcomes		Enroll 6 Wk 3M 6M 9M
Psychological Health		
Mental HRQoL	PROMIS [®] (SFv1.2- Global Health)	X X X X X
Depressive Cognitions	Depressive Cognitions Scale	X X X X X
Depressive Symptoms	PROMIS [®] (SFv1.0- Depression 8a)	X X X X X
